6.3 SAFETY ANALYSES

Safety analyses will be performed on the safety-evaluable population, which is defined as patients who receive any amount of study drug. Subgroup safety analyses by tumor type cohort will also be conducted as appropriate.

Study treatment exposure (such as treatment duration, total dose received, and number of cycles and dose modifications) will be summarized with descriptive statistics.

All adverse events, serious adverse events, adverse events leading to death, adverse events of special interest, and adverse events leading to study treatment discontinuation, occurring on or after the first dose of study treatment (i.e., treatment-emergent adverse events) will be summarized by mapped term, appropriate thesaurus level, and toxicity grade. For events of varying severity, the highest grade will be used in the summaries. Deaths and cause of death will be summarized.

Laboratory toxicities will be summarized by NCI CTCAE grade.

6.4 PHARMACOKINETIC ANALYSES

Individual and mean C_{max} of atezolizumab on Day 1 of Cycle 1 and Day 1 of Cycle 4 will be summarized. In addition, C_{min} of atezolizumab on Day 1 of Cycles 2, 3, 4, 8, 12, and 16 and every 8 cycles thereafter, at study drug discontinuation, and after washout will be summarized. Atezolizumab AUC for serum concentration-time profile in Cycle 1 will be estimated using a population PK model, as appropriate. Descriptive statistics will include mean, median, range, standard deviation, *coefficient of variation*, *geometric mean*, and *geometric mean coefficient of variation* as appropriate. After a minimum of 20 patients have completed Cycle 1, interim PK and safety analyses will be conducted. Relationships between PK and PD biomarkers may be explored using population PK and/or PD modeling approaches, as appropriate. Details regarding the modeling and simulations will be described in a separate Modeling and Simulations Data Analysis Plan prior to the modeling.

6.5 IMMUNOGENICITY ANALYSES

The immunogenicity analyses will include patients with at least one ATA assessment. The numbers and proportions of ATA-positive patients and ATA-negative patients during both the treatment and follow-up periods will be summarized. Patients are considered to be ATA positive if they are ATA negative *or missing* at baseline but develop an ATA response following study drug administration (treatment-induced ATA response), or if they are ATA positive at baseline and the titer of one or more post-baseline samples is at least 4-fold greater (i.e., ≥ 0.60 titer units) than the titer of the baseline sample (treatment-enhanced ATA response). Patients are considered to be ATA negative if they are ATA negative *or missing* at baseline and all post-baseline samples are negative, or if they are ATA positive at baseline but do not have any post-baseline samples with a titer that is at least 4-fold greater than the titer of the baseline sample (treatment unaffected).

The relationship between ATA status and safety, efficacy, PK, and biomarker endpoints will be analyzed and reported descriptively via subgroup analyses.

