3.4.3 Immunogenicity Outcome Measure

The immunogenicity outcome measure for this study is as follows:

- Incidence of ATAs during the study relative to the prevalence of ATAs at baseline

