Appendix 1 Schedule of Assessments (cont.)

Day	Screening Period ^a	Treatment Period														Follow-Up Period ^b				
		C1			C2		C3	C4	C5	C6	C7	C8	C9	C10	C11	C12+	Study Drug Discont. ^c	Day 90 Follow-up ^c	Long-Term Follow-Up ^d	
	1	8	15	1	ATRT Only		1	1	1	1	1	1	1	1	1					
	-28 to -1	1	8	15	1	8	15	1	1	1	1	1	1	1	1	1				
Tetanus toxoid antibody titer ^z		x																x		
Auto-antibody testing ^{aa}		x																		
Survival assessment																			x	x
Optional RCR tumor tissue sample and corresponding blood sample ^{bb, cc, dd}		x			x													x		

ATA=anti-therapeutic antibody; C=cycle; CT=computed tomography; discontin.=discontinuation; eCRF=electronic Case Report Form; FDG-PET=fluorodeoxyglucose-positron emission tomography; HIV=human immunodeficiency virus; MIBG=metaiodobenzoguanine; MUGA=multigated acquisition scan; MRI=magnetic resonance imaging; PK=pharmacokinetic; RCR=Roche Clinical Repository; TBNK=T, B, and natural killer (cells).

Notes: All assessments should be performed within 3 days of the scheduled date (excluding Day 1 of Cycle 1), unless otherwise specified. On treatment days, all assessments should be performed prior to dosing, unless otherwise specified. Cycles are 3 weeks in length. Atezolizumab infusion may be delayed up to 5 days to accommodate holidays, weekends, and other patient obligations.

Assessments shaded in gray should be performed as scheduled, but the associated data do not need to be recorded on the eCRF (except in the case of ATRT neurologic examinations, an adverse event, or a pregnancy).

^a Results of standard-of-care tests or examinations performed prior to obtaining informed consent and within 28 days prior to Day 1 of Cycle 1 may be used; such tests do not need to be repeated for screening. Informed consent must be documented before any study-specific assessments are performed.

^b In situations where it is either unsafe or not in the best interest of the patient to complete follow-up assessments after study drug discontinuation, survival data only may be submitted during the follow-up period with approval of the Medical Monitor.

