Appendix 1 Schedule of Assessments (cont.)

-
- ^c Patients who discontinue study drug should return to the clinic for study drug discontinuation visits within 28 days of the last dose of atezolizumab. This may be done at the clinical visit where clinical or radiographic progression is first noted). A follow-up visit should also be done 90 (\pm 10) days after the last dose of study drug. If treatment with another anti-cancer treatment is scheduled to begin within 90 days after the last dose of study drug, this visit should be performed before the patient starts the other treatment, if possible. *If the day 90 visit is done after initiation of another anti-cancer treatment, only PK and/or ATA blood samples and those laboratory tests needed to monitor for the resolution of adverse events need to be drawn.*
- ^d Long-term follow-up information will be collected every 3 months during the first two years (Years 1 and 2), every 6 months during Year 3, and yearly until study termination by Sponsor, death, loss to follow-up, or withdrawal of consent, whichever occurs first.
- ^e A tumor specimen and associated pathology report must be confirmed to be available prior to patient participation in any study-specific screening procedures and must be shipped within 30 days of first dosing. See Section 4.5.6 for details on sample collection.
- ^f Medical history includes clinically significant diseases, surgeries, cancer history (including prior cancer therapies, current cancer stage, and procedures), menstrual history, fertility history, and puberty history. Demographic data will include age, sex, and self-reported race/ethnicity as permitted by local regulatory authorities.
- ^g All females of childbearing potential must undergo a serum pregnancy test within one week of the initial dose. Urine or serum pregnancy tests must be performed prior to the start of all subsequent cycles.

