Appendix 2 Schedule of Pharmacokinetic, Pharmacodynamic, and Immunogenicity Assessments

Visit	Timepoint	Sample Type
Cycle 1, Day 1	Prior to the infusion	Serum for atezolizumab PK and ATA ^a EDTA plasma and whole blood for PD
	30 (± 10) min after the end of the infusion	Serum for atezolizumab PK
Cycle 1, Day 8	Any time during visit	Serum for atezolizumab PK
Cycle 2, Day 1	Prior to the infusion ^b	Serum for atezolizumab PK and ATA ^a Plasma and whole blood for PD
Cycle 3, Day 1	Prior to the infusion ^b	Serum for atezolizumab PK and ATA ^a Plasma and whole blood for PD
Cycle 4, Day 1	Prior to the infusion ^b	Serum for atezolizumab PK and ATA ^a
	30 (± 10) min after the end of the infusion	Serum for atezolizumab PK
Cycle 8, Day 1	Prior to the infusion ^b	Serum for atezolizumab PK and ATA ^a Plasma and whole blood for PD
Cycle 12, Day 1	Prior to the infusion ^b	Serum for atezolizumab PK and ATA ^a Plasma and whole blood for PD
Day 1 of Cycle 16 and every 8 cycles thereafter	Prior to the infusion ^b	Serum for atezolizumab PK and ATA ^a Plasma and whole blood for PD
Study drug discontinuation visit	Any time during visit	Serum for atezolizumab PK and ATA ^a Plasma and whole blood for PD
At least 90 days (but no more than 150 days) after last dose of study drug	Any time during visit	Serum for atezolizumab PK and ATA ^a Plasma and whole blood for PD

ATA=anti-therapeutic antibody; PD=pharmacodynamic; PK=pharmacokinetic.

^a Serum samples will be split into 2 × 500 µL serum aliquots, one for PK and one for ATA.

^b Blood draws can occur up to 2 days prior to infusion.

Appendix 3

Modified International Neuroblastoma Response Criteria

Below response assessment is modified from the original INRC publication in 1993.

DEFINITION OF MEASURABLE (EVALUABLE) DISEASE ON CT/MRI SCAN

The presence of at least one lesion that can be accurately measured in at least one dimension with the longest diameter at least 20 mm. With a spiral CT scan, lesions must be at least 10 mm. The investigator will identify up to 10 measurable target lesions to be followed for response. Note that bone lesions will be considered as non-target lesions for evaluation of CT/MRI response since they will be evaluated with MIBG scans.

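### Section 6.5 uses one ATA analysis set that admits patients with only a baseline sample, so reported ATA incidence is slightly diluted and untested patients can fall into the ATA-negative group

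*Combined protocol and SAP*

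**What the plan says.** Section 6.5 sets the population in one sentence: "The immunogenicity analyses will include patients with at least one ATA assessment". It then commits to this summary: "The numbers and proportions of ATA-positive patients and ATA-negative patients during both the treatment and follow-up periods will be summarized". No other denominator is given.

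A patient is ATA positive through a treatment-induced response (baseline negative or missing, then a response after dosing) or a treatment-enhanced one (baseline positive, then at least a 4-fold titer rise). A patient is ATA negative by either of two limbs:

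- Baseline negative or missing: the condition is being so "at baseline and all post-baseline samples are negative".
- Baseline positive: the condition is that such patients "do not have any post-baseline samples with a titer that is at least 4-fold greater than the titer of the baseline sample". The plan labels these patients treatment unaffected.

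Section 3.4.3 gives the single immunogenicity outcome measure: "Incidence of ATAs during the study relative to the prevalence of ATAs at baseline". Section 6.5 also plans descriptive subgroup analyses of safety, efficacy, PK and biomarker endpoints by ATA status.

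In Appendix 2, samples listed as "Serum for atezolizumab PK and ATA" are drawn before the infusion on Day 1 of Cycles 1, 2, 3, 4, 8, 12 and 16 and every 8 cycles after that, at the discontinuation visit, and between 90 and 150 days after the last dose. The Cycle 1 Day 8 sample is for PK only.

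**The concern.** The outcome measure compares two quantities that need different denominators. Baseline prevalence needs a baseline result. Incidence on study needs at least one result after dosing. Section 6.5 supplies one set for both and does not require a post-baseline sample. It deals openly with missing baseline samples but not with missing post-baseline ones, and it has no not-evaluable category. By contrast, Section 6.6.1 does say how patients with no post-baseline tumor assessment are treated: they count as non-responders.

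Two things are at stake. First, the headline ATA proportion is pulled down. Section 3.3.3 says there are no pediatric immunogenicity data for checkpoint inhibitors, and Section 3.3.1 raises ATA-related loss of exposure as a possibility, especially in the lightest children. Second, patients never tested after dosing can enter the ATA-negative group in the subgroup analyses. Early drop-outs lacking both a post-baseline scan and a post-baseline ATA sample would be non-responders counted as ATA negative, which would lower the response rate in that group and could hide an adverse effect of ATAs on response.

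**Working it through.** The plan states no expected ATA rate, no share of patients without a post-baseline sample and no confidence interval method for ATA incidence. There is no figure of its own to reproduce.

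**Step 1: apply the rules to a patient with a baseline sample and nothing afterwards.**

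| Baseline | In the set? | Can be ATA positive? | Meets the ATA-negative rule? |
|---|---|---|---|
| Positive | Yes | No; needs a later titer | Yes, literally: no later sample shows a 4-fold rise |
| Negative | Yes | No; needs a later response | Only vacuously: there are no later samples. Otherwise no category applies |

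The dilution of the positive proportion does not depend on how the baseline-negative row is read. Either way the patient is in the denominator and cannot be in the numerator. The reading matters for the ATA-negative count and for the subgroups.

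**Step 2: size of the dilution.** Let N be the size of the set, m the baseline-only share, and p the positive rate among patients with a post-baseline sample. Positives number p × N × (1 − m), so

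reported proportion = p × N × (1 − m) / N = p × (1 − m), and the understatement is p × m.

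Both m and p are assumptions:

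| p | m | Reported, p(1 − m) | Understatement, p × m |
|---|---|---|---|
| 20% | 5% | 19.0% | 1.0 point |
| 20% | 10% | 18.0% | 2.0 points |
| 30% | 5% | 28.5% | 1.5 points |
| 30% | 10% | 27.0% | 3.0 points |

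Over a wider range, m of 5–20% and p of 10–40%, the understatement runs from 0.10 × 0.05 = 0.5 to 0.40 × 0.20 = 8 points. Nothing in the documents supports the upper end.

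**Step 3: compare with sampling error.** Take N = 100, the approximate planned enrolment, with Clopper–Pearson 95% intervals.

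- p = 20%, m = 10%: 18/100 = 18.0% (11.0 to 26.9; half-width 15.9/2 ≈ 8 points) against 18/90 = 20.0% (12.3 to 29.8; half-width 17.5/2 ≈ 9 points). The shift is 2 points.
- p = 30%, m = 10%: 27/100 = 27.0% (18.6 to 36.8; half-width 18.2/2 ≈ 9 points) against 27/90 = 30.0% (20.8 to 40.6; half-width 19.8/2 ≈ 10 points). The shift is 3 points.

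**Step 4: can baseline-only patients arise?** The first scheduled post-baseline ATA sample is Cycle 2 Day 1, three weeks after the first dose. Death, withdrawal of consent or loss to follow-up before then leaves a baseline-only patient unless a later sample is taken. Section 4.6.1 stops follow-up once consent is withdrawn and does not replace withdrawn patients. Appendix 1 also allows that "survival data only may be submitted during the follow-up period with approval of the Medical Monitor". Under the blood-volume limits in Section 4.5.6, clinical laboratory tests take precedence over PK and immunogenicity samples, which bears most on the smallest children.

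**The case against.** The strongest reply is that Section 6.5 is merely silent here. A rule about all post-baseline samples ordinarily presupposes that some exist, and the sentence on the treatment and follow-up periods points the same way. A reader might infer that the plan expressly classes every untested patient as ATA negative. The text does not go that far: it is literally so only for baseline-positive patients. That part of the reply stands. It does not remove the problem, because the alternative leaves baseline-negative patients in the denominator with no category.

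The broad set also has a sensible purpose. It covers patients needed for baseline prevalence as well as those whose baseline sample is missing. That is fair, and it places the gap in the missing incidence denominator rather than in the admission rule.

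The sampling plan also works against large m. Appendix 1 says: "Patients who discontinue study drug should return to the clinic for study drug discontinuation visits within 28 days of the last dose of atezolizumab". That visit carries an ATA sample, as does the 90–150 day sample. If the Day 90 visit follows new anti-cancer therapy, PK and/or ATA samples are still drawn. Residual PK serum may be used for additional ATA testing (Section 4.5.6), and entry requires a life expectancy of at least 3 months. All of this stands and argues for a small m, though not for zero.

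Finally, no formal hypothesis test is planned, the subgroup analyses are descriptive, and no stated dosing, expansion or stopping rule depends on ATA incidence. That limits the consequences. It does not excuse a proportion whose denominator includes patients who could not have contributed an event.

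**Conclusion.** The point holds as a correctable flaw in the definition of the analysis set. If there is at least one baseline-only patient and at least one ATA-positive patient, the proportion calculated on the set as written falls below the rate among patients sampled after dosing. The relative shortfall equals m. With m assumed at 5–10% and the rate at 20–30%, that is about 1 to 3 percentage points, smaller than the interval half-width of roughly 8 to 10 points at about 100 patients.

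A reader might infer that the true pediatric ATA incidence is understated by a known or large amount. The documents do not support that. Both inputs are assumptions, and the comparison is with the rate among sampled patients, which equals the true incidence only if unsampled patients would have had the same rate. The misclassification in the ATA-status subgroups has the same source, and its size is equally undetermined. The change is worth making because this is the only immunogenicity outcome and the remedy is nearly free, not because a material bias has been shown.

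**What to change.** In Section 6.5, replace the single set with two denominators and one count:

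- Report baseline ATA prevalence among patients with a baseline ATA sample.
- Report treatment-emergent ATA incidence, and all analyses by ATA status, among treated patients with at least one post-baseline ATA sample.
- Report the number of patients with no post-baseline ATA sample as not evaluable, in neither the positive nor the negative group.

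The cost is a sentence or two in the plan, with no new samples, visits or data. The denominator becomes slightly smaller and the interval slightly wider: in the 18-positive example the width goes from 15.9 to 17.5 points. The result is a complete-case estimate, so the not-evaluable count should appear beside it to let readers judge how much it could matter.

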3.4.6 Exploratory Outcome Measures

The exploratory outcome measures for this study are as follows:

- Descriptive analyses of PD-L1 expression (as defined by immunohistochemistry [IHC] score), infiltrating T-cell activity, T-cell subpopulations, and B-cell and NK cell absolute counts in baseline tumor samples
- Correlation between PD-L1 expression (both overall expression and by tumor type) at baseline, as defined by IHC score, and efficacy outcome measures
- Levels of potential PD biomarkers (including but not limited to cytokines, ctDNA concentration, and T-cell subpopulations) will be measured in plasma and whole blood collected at baseline; at Cycles 1, 2, 3, 8, and 12 and every 8 cycles thereafter; and at the time of progressive disease.

- Correlation between non-inherited and inherited biomarkers in plasma, whole blood, or tumor tissue (including but not limited to PD-L1, PD-1, CD4, CD8, FoxP3, cytokines, ctDNA concentration, ctDNA mutations, and T-cell receptor sequencing) and safety, PK, or efficacy outcome measures
- Changes in T, B, and NK cell numbers (TBNK assay) in whole blood
- Correlation between ATA status and PK, PD, safety, or efficacy outcome measures
- Descriptive analyses of PD-L1 expression (as defined by IHC score), infiltrating T-cell activity, T-cell subpopulations, and B-cell and NK cell absolute counts in any available tumor samples obtained at the time of progressive disease

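### Section 6.5 compares efficacy from first dose by an ever-positive ATA status that builds up with time on treatment; in expectation this favors ATA-positive patients, by an amount set by an ATA onset that the documents do not give

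*Combined protocol and SAP*

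**What the plan says.** - **Classification (6.5).** A patient who is ATA negative or missing at baseline becomes positive on any ATA response after dosing. A patient positive at baseline becomes positive if "the titer of one or more post-baseline samples is at least 4-fold greater" than at baseline. A baseline-negative patient stays negative only if "all post-baseline samples are negative". No time window is set.
- **Population (6.5).** "The immunogenicity analyses will include patients with at least one ATA assessment". That assessment need not be post-baseline.
- **Comparison (6.5).** "The relationship between ATA status and safety, efficacy, PK, and biomarker endpoints will be analyzed and reported descriptively via subgroup analyses". Section 3.4.6 lists it among the exploratory measures: "Correlation between ATA status and PK, PD, safety, or efficacy outcome measures".
- **On-treatment draws (Appendix 2).** Pre-dose on Day 1 of Cycles 2, 3, 4, 8 and 12, then "Day 1 of Cycle 16 and every 8 cycles thereafter".
- **Off-treatment draws.** ATA serum is taken at the discontinuation visit and again 90 to 150 days after the last dose. Appendix 1, footnote c, says: "Patients who discontinue study drug should return to the clinic for study drug discontinuation visits within 28 days of the last dose of atezolizumab". The same footnote keeps ATA sampling at Day 90 even after another anti-cancer treatment has begun.
- **Outcome times (6.6.1, 6.6.2).** PFS and OS start at first dose.
- **Treatment duration (3.1).** Treatment continues while there is clinical benefit, for up to 8 months, and longer with Medical Monitor approval.

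No landmark, time-dependent status, minimum sampling or adjustment for time on treatment is given.

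**The concern.** A patient has to remain alive, and for the later draws on treatment, to be given the chance to be found positive. Status is thus partly decided by the outcome that it is later used to explain. Comparing the groups from first dose credits the positive group with the event-free time that was needed to become positive (guarantee-time, or immortal-time, bias).

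ORR is exposed as well. The first scheduled scan falls in the last week of Cycle 2 (4.5.5.1), and a response must be confirmed at least 4 weeks later (6.6.1). A response first seen on that scan is confirmed no earlier than about week 9, when Cycle 4 Day 1 falls. Responders on treatment therefore reach draws that early progressors do not.

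The question matters. Section 3.3.3 says that no pediatric immunogenicity data exist for checkpoint inhibitors. Section 3.3.1 says that ATA may worsen low exposure in the lightest children. A comparison tilted toward ATA being harmless could give false reassurance.

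**Working it through.** The plan states no ATA incidence, effect size or power, so there is no figure to reproduce.

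**1. Draw counts from Appendix 2.** As an illustration, assume a 10% chance of a positive result at each draw and full attendance, so P(ever positive) = 1 − 0.9^n.

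| Last cycle received | On treatment | Off treatment | n | P(ever positive) |
|---|---|---|---|---|
| 1 | 0 | 2 | 2 | 19% |
| 2 | 1 | 2 | 3 | 27% |
| 4 | 3 | 2 | 5 | 41% |
| 12 | 5 | 2 | 7 | 52% |
| 16 | 6 | 2 | 8 | 57% |

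Mix equal numbers stopping in Cycle 2 and in Cycle 12. Long-treated patients then make up 0.522/(0.522 + 0.271) = 66% of positives and 0.478/(0.478 + 0.729) = 40% of negatives, although ATA does nothing.

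**2. Simulated PFS hazard ratio, ever-positive vs never-positive, no true ATA effect, sensitive assay.** Everything except the draw and scan schedules is assumed.

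| Model | Assumptions | PFS HR |
|---|---|---|
| A | Progression seen continuously; median PFS 1.4–3 months; 30–40% can seroconvert; mean onset 1.5–3 months; sample at progression; washout sample in 0–60% of survivors | 0.56–0.83 |
| B | 80% of progressions found at scheduled scans; median PFS 1.4 or 3 months; 35% can seroconvert; washout attendance 60–100% | onset 3 months: 0.78–0.84; 1–1.5 months: 0.86–0.94; 0.75 months or less: 0.92–0.99 |
| C, accruing | 10% responders (median PFS 12 months), others 1.5 months; ATA accrues at 3–20% per cycle; 18-month cutoff | 0.37–0.46 |
| C, slower disease | Median PFS 3–5 months, 10–40% responders | 0.27–0.37 |
| C, 6-month cutoff | As C, ATA accruing at 10% per cycle | 0.61–0.67 |
| C, early | All ATA appears by Cycle 2–3; 18-month cutoff | 0.88–0.96 |

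In a further 48 scenarios every PFS HR was below 1; those with scheduled scans gave 0.76–0.98. In model C, OS HR was 0.36–0.50 (accruing) or 0.87–0.95 (early). In the accruing case ORR was 13–30% in positives against 1–5% in negatives. Patients with only a baseline sample, counted as negative, were 1–5% of the total, all early deaths. In simulated 100-patient trials under model A, the HR fell below 1 in 79–99% of runs.

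**3. Masking (model C, true harmful PFS HR 1.5).** The naive HR was 0.43–0.51 if ATA accrues and 1.04–1.12 if onset is early.

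**4. Assay stress test (model C, no true effect).** On-drug sensitivity was cut to 50%, 20% and 5%. PFS HR passed 1 clearly only at 5% sensitivity with a 6-month cutoff (up to 1.40); at 20% the highest value was 1.02. ORR could also reverse, only at 20% or lower. OS HR stayed below 1 throughout.

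**5. Does a landmark remove the bias?** With no true effect, Cycle 3 Day 1 gave PFS HR 0.99–1.01. Cycle 4 Day 1 gave PFS HR 0.99–1.01, OS HR 0.95–1.01 and, for example, ORR 15.3% vs 15.5%. With a true HR of 1.5, the Cycle 4 landmark gave 1.12–1.21: right direction, diluted size.

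**6. What the landmark costs.** Week 6 is 42/30.4 = 1.38 months. Under model A, the share of eventual converters who have converted by then is 1 − exp(−1.38/3) = 37% to 1 − exp(−1.38/1.5) = 60%. The share already progressed is 1 − 2^(−1.38/3) = 27% to 1 − 2^(−1.38/1.4) = 50%. Of 100 patients, about 100 × 0.50 × 0.30 × 0.37 = 6 to 100 × 0.73 × 0.40 × 0.60 = 18 would be landmark-positive.

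**7. Is a within-patient before/after PK comparison sound?** The amendment rationale equates 5 months with five half-lives, so about 1 month each. With 3-weekly dosing and one compartment, the fraction remaining per cycle is r = 2^(−21/30.4) = 0.62. Relative to Cycle 2, Cmin at Cycle 4 is 1 + r + r² = 2.0, and at Cycle 8 it is (1 − r⁷)/(1 − r) = 2.5. Accumulation alone would hide a fall in exposure caused by ATA.

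**The case against.** The comparison is an exploratory objective (2.6) and measure (3.4.6), reported descriptively, and 6.1 plans no formal testing. The immunogenicity outcome measure itself is ATA incidence (3.4.3). Section 6.5 names no hazard ratio, so the ratios above are only a yardstick for whatever display is used. All of this stands and limits the consequence to interpretation. It does not remove the bias, since Kaplan-Meier curves, medians and response rates by ever-positive status inherit it.

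Three stronger readings are tempting, and the documents do not support them:

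- **Only long-treated patients complete the sampling, and a patient stopping in Cycle 2 has one or two chances.** This is true only of the later on-treatment draws. That patient has three scheduled chances: Cycle 2 Day 1, discontinuation and washout. These draws reduce the imbalance but do not remove it, because patients who die early miss them.
- **ATA-positive patients are bound to look better.** The bias is in expectation. Its size turns on ATA onset and assay performance, for which the documents give no figures, and chance can hide or mimic it in about 100 patients. Scheduled scans, and treatment beyond progression (3.3.4, 4.5.5.2) with the sampling that follows it, also soften it.
- **The study's conclusions or dose decisions are compromised.** No dose, expansion or stopping rule is stated to use this comparison.

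For adverse events, the direction rests on reasoning, not calculation: 6.3 summarizes events without exposure adjustment, and longer treatment brings both more ATA samples and more events.

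**Conclusion.** The point holds as a bias in an exploratory analysis that nothing in the documents corrects. With no true ATA effect and a sensitive assay, the expected PFS hazard ratio lies below 1: about 0.9 to just below 1 if ATA appears early, scans are on schedule and washout attendance is high; 0.56–0.83 under model A; about 0.3–0.5 if ATA accrues each cycle and there are some long responders. OS and ORR lean the same way, and a truly harmful ATA effect can be hidden or look like benefit. Very poor on-drug assay sensitivity could shrink the bias or, in extreme cases, reverse it for PFS. PFS medians, responder share, ATA onset, washout attendance and assay sensitivity are all assumptions. The change is worth making before analysis because it is cheap and bears on a question for which the protocol says pediatric data are lacking.

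**What to change.** Amend 6.5 as follows:

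- **PFS and OS:** analyze ATA as a time-dependent status, negative until the date of the first qualifying sample. Samples taken after a PFS event then cannot reclassify the time before it.
- **Kaplan-Meier and ORR displays:** use a landmark at Cycle 3 or Cycle 4 Day 1, chosen in advance. Take status from samples up to that day, include event-free patients only, and count time from the landmark.
- **Negative class:** require at least one post-baseline ATA sample. Report ATA onset time and the number of samples per patient.
- **Adverse events:** report rates per patient-time before and after first positivity.
- **PK:** compare Cmin by ATA status at the same cycle, not within patient before and after positivity.

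The cost is SAP wording and light programming, with no new visits or samples. The landmark display drops early progressors, counts later converters as negative and leaves few positive patients (roughly 6 to 18 of 100 at Cycle 3 under model A). It should therefore stay descriptive, beside the time-dependent analysis, which keeps everyone.
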